Theoretically, coffee consumption is associated with increased brain function. "Coffee is also well-known for its positive effects on mental alertness and psychological lift, benefits often attributed to caffeine content. Indeed, frequent low doses of caffeine counter the effects of extended wakefulness" (Taylor & Demming-Adams, 2007). Additionally, Warner and colleagues (2018) state that murine models have demonstrated an enhanced speed of recovery from general anesthesia, however this phenomenon has not been examined in humans. Therefore, Warner's team (2018) conducted one of the first (if only) studies examining the association between caffeine administration and changes in sedation scores among 151 heavily sedated patients in a PACU. Following administration of IV caffeine, RASS scores increased and no adverse respiratory events were noted following caffeine administration. The data suggested that IV caffeine may enhance speed of recovery from general anesthesia. Warner and colleagues' study provides preliminary evidence that coffee consumption may increase speed of recovery. Once again, no studies have examined whether providing coffee to patients postoperatively would decrease the length of stay in the PACU compared to not providing coffee.

Research Plan

• Study Design

A randomized, non-blinded, controlled study will be conducted, with two arms. Subjects will be randomized into one of the two following arms:

- Arm 1: Subjects will receive coffee while in the PACU
- Arm 2: Subjects will NOT receive coffee in PACU
- Setting for the study

The study will take place in the Bethesda North Minimally Invasive Surgery Center. This unit consists of 3 operating rooms and 7 postoperative recovery bays. The team members on this unit provide care for patients undergoing minimally invasive outpatient procedures including (but not limited to) Herniorrhaphy Repairs, Laparoscopic Cholecystectomies, Lipoma Removals, Hysteroscopies, Uterine Ablations, Bladder Slings, Female Sterilization, Breast Reductions and Augmentations, and other Plastic Surgery. There are approximately 10-20 surgeries performed in this setting each day. We are a 3 OR Suite facility with 6 Pre-Op Bays and 7 Recovery Bays.

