In April 2022, the Bethesda Surgery Center was added as a second recruitment site. This unit consists of 4 operating rooms and 8 postoperative recovery bays. The team members on this unit provide care for patients undergoing minimally invasive outpatient procedures including (but not limited to) Herniorrhaphy Repairs, Laparoscopic Cholecystectomies, Hemorrhoidectomies, Lipoma Removals, Eye Muscle Repair, Breast Reductions and Augmentations, Abdominoplasty, and other Plastic Surgery. There are approximately 10-20 surgeries performed in this setting each day. We are a 4 OR Suite facility with 6 Pre-Op Bays and 8 Recovery Bays.

• Participants

This study will enroll 300 subjects who meet the inclusion/exclusion criteria.

Inclusion criteria:

- 1. 18 years old or older
- 2. Admitted to Bethesda North Minimally Invasive Surgery Center or the Bethesda Surgery Center
- 3. Reports to consume at least one cup of coffee a day for at least 5 days in a week

Exclusion Criteria

- 1. History of PONV
- 2. Pre-existing cardiac arrhythmias
- 3. History of seizure disorder
- 4. Pregnant

Withdraw Criteria (patients who meet inclusion/exclusion criteria and consent to participate, but then develop one of these criteria, will be removed from the study)

- 1. Participants in the intervention arm who fail to drink at least 50 ml of coffee
- 2. Participants in the intervention arm who experience PONV prior to coffee consumption
- 3. Participants in the control arm who experience PONV prior to or during consenting process (consenting process will stop if patient begins experiencing PONV)

Sample Size Determination: A power analysis was conducted using G*Power (version 3.1.9.2). The primary outcome variable (length of stay) was used with a small-medium

effect size (0.3), power of 0.8, and level of significance 0.05. It was determined that 139 patients would be needed in each group, for a total sample size of 278 patients. Therefore, we plan to enroll approximately 300 patients to allow for missing data and patient withdrawals.

• Data Collection

Before the study begins, the study staff will provide education to all of the nurses working in the department involved in patient care. This education will include information about the study design, the intervention, and the inclusion/exclusion criteria.

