Patients who meet the inclusion criteria will be approached by a member of the study team. The study team member will describe the study and answer any questions the patient has. If the patient is interested in enrolling in the study, they will be asked to review and sign an Informed Consent Form and a HIPAA Authorization Form. Personal health information, including name and date of birth, are recorded on the informed consent form and/or HIPAA Authorization Form.

After the patient provides written informed consent, the study team member will remove the next envelope out of a box of prefilled and sealed opaque envelopes. The envelope will provide the Subject ID number to be used on all study-related documentation and the study Arm that the patient has been randomized to.

• Intervention or experimental aspect of the study

Patients randomized to Arm 1 will receive coffee in a Styrofoam cup at a temperature of 125 degree Fahrenheit or less (Brown & Diller, 2008). Coffee will be offered to the patient in the PACU once the patient's gag reflex has been restored following their procedure. Volume of estimated coffee consumption will be measured using a sample scale (with a maximum of 300mL of coffee offered). Patients randomized to Arm 2 will not be offered coffee while in the PACU.

A data collection form will accompany patient to the PACU designating them as a study participant. Data will be recorded directly on this form and collected by a study team member after the patient is discharged.

Independent variable:

• Whether patient consumed part or all of the coffee in the PACU or not

Dependent variables:

- o Primary outcome variable Patient's LOS in the PACU
- Secondary outcome variables:
 - Whether the patient experienced PONV
 - Patient satisfaction

Potential confounding variables:

- o How many minutes after entering PACU patient consumed coffee
- o How much coffee patient consumed

• Statistical Analysis

Data will be recorded on paper data collection forms with only subject ID and no identifiers. Data from these forms will be entered into a password protected database. Only study team members will have access to the database. No personal information will be entered into the electronic database. Data will undergo range checks when entered into the database, and quality control procedures will be performed to ensure accuracy of the data in the electronic database.

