Statistical analyses will be performed using SPSS statistical software. Descriptive statistics (frequencies for categorical data; means and standard deviations and ranges for continuous data) will be used to describe the sample. The following analyses will be performed to address each hypothesis:

Hypothesis 1: Patients who self-identify as coffee drinkers who receive coffee postoperatively will experience a shorter length of stay in the PACU compared to patients who self-identify as coffee drinkers and do not receive coffee postoperatively.

To compare the effects of the intervention, an independent samples t-test will be used to compare mean length of stay in the PACU for patients who received coffee to the mean length of stay in the PACU among patients who did not receive coffee. A level of significance of α =0.05 will be used.

Hypothesis 2: Patients who self-identify as coffee drinkers who receive coffee postoperatively will experience a lower occurrence of postoperative nausea and vomiting in the PACU compared to patients who self-identify as coffee drinkers and do not receive coffee postoperatively.

To compare the effects of the intervention, a Chi Square test will be used to compare occurrence of postoperative nausea and vomiting for patients who received coffee to patients who did not receive coffee. A level of significance of α =0.05 will be used.

Hypothesis 3: Patients who self-identify as coffee drinkers who receive coffee postoperatively will report higher patient satisfaction compared to patients who self-identify as coffee drinkers and do not receive coffee postoperatively.

To compare the effects of the intervention, an independent samples t-test will be used to compare mean patient satisfaction for patients who received coffee to the mean patient satisfaction among patients who did not receive coffee. A level of significance of α =0.05 will be used.

Ethical Considerations

• Informed consent

All study staff will complete CITI training. A study staff member will meet with potentially eligible patients and describe the study and answer any questions. If the patient is interested and meets all the inclusion/exclusion criteria, the study staff will review the *Informed Consent Form* and *HIPAA Authorization* and obtain written informed consent. Patients will receive a copy of their signed Informed Consent form and HIPAA Authorization.

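### The protocol implies two incompatible times for consent and ties envelope opening to no later event; if consent is preoperative, early PONV is removed from the coffee arm only

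*Combined protocol and SAP*

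**What the plan says.** The protocol describes consent twice, each time without a time or place. Data Collection says: "Patients who meet the inclusion criteria will be approached by a member of the study team". The informed consent text under Ethical Considerations says: "A study staff member will meet with potentially eligible patients and describe the study and answer any questions". Allocation, by envelope, is the next step: "After the patient provides written informed consent, the study team member will remove the next envelope out of a box of prefilled and sealed opaque" … Each envelope supplies both the Subject ID and the arm.

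Two other places hint at timing:

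- Withdraw Criteria, criterion 3: "Participants in the control arm who experience PONV prior to or during consenting process (consenting process will stop if patient begins experiencing PONV").
- Intervention or experimental aspect of the study: "A data collection form will accompany patient to the PACU designating them as a study participant".

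The lead-in to the withdrawal criteria limits them to eligible patients who "consent to participate, but then develop one of these criteria, will be removed from the study". Criterion 2 removes coffee-arm patients who have PONV before drinking any coffee.

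Under Study Design: "A randomized, non-blinded, controlled study will be conducted, with two arms". Coffee is first offered in the PACU, after the gag reflex has returned. The primary outcome is length of stay (LOS) in the PACU, with no stated start or stop. PONV is a secondary outcome, compared by a chi-square test (Hypothesis 2).

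**The concern.** The moment of allocation decides which events come before randomisation and which come after. Events before it can be excluded without harm, because neither arm exists yet. Events after it must be counted in the same way in both arms. A plan that leaves this moment open cannot say which PONV episodes belong to the comparison.

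The interval also matters because the trial is unblinded. Nothing distinguishes the arms until coffee can be offered, so revealing the arm earlier serves no purpose and leaves room for care, or the decision to stay in the trial, to depend on it. A second site was added in April 2022, so two units now work from text that supports two sequences.

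**Working it through.** **1. The two cues side by side.** Criterion 3 has PONV occurring before or during consent, and "consenting process will stop if patient begins experiencing PONV". Postoperative nausea can do that only if consent follows surgery. The travelling form marks the patient as a participant on the way to the PACU, so consent has already been given. Both cannot be true of the same patient, and no other section settles it.

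**2. Criterion 3 on its own terms.** It names control-arm participants during consent. The arm comes from an envelope drawn after consent, so no patient has an arm at that point. The criterion also conflicts with its lead-in, which covers only patients who have already consented.

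**3. If consent is before surgery.** PONV cannot precede consent, so criterion 3 never applies. Criterion 2 still does, in the coffee arm only. Let *e* be the proportion with PONV before the coffee point and *l* the proportion with PONV only later. Suppose coffee has no effect and removed patients are left out of the analysis. Then:

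- control shows *e* + *l*
- coffee shows *l* / (1 − *e*)

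The documents give no PONV rates, so these are assumed:

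| *e* | *l* | Control | Coffee | False difference |
|---|---|---|---|---|
| 10% | 10% | 20% | 0.10/0.90 = 11.1% | 8.9 points |
| 5% | 5% | 10% | 0.05/0.95 = 5.3% | 4.7 points |

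The error favours coffee, the direction of Hypothesis 2.

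For LOS, if patients with early PONV stay Δ longer on average than the others, removing them from one arm shortens the coffee mean by *e*Δ relative to control. To produce the whole planned effect of 0.3 SD, Δ would have to be 0.3/0.10 = 3 SD at *e* = 10%, or 0.3/0.05 = 6 SD at *e* = 5%. This route can contribute to an apparent LOS benefit but is unlikely to create all of it.

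**4. If consent is in the PACU.** The asymmetry in PONV shrinks to the time between envelope and coffee, but consent now falls inside the measured stay.

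The plan's own figure comes first. Inputs from Sample Size Determination: effect size 0.3, power 0.8, significance level 0.05, 139 per group.

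- One-sided: 2(1.645 + 0.842)²/0.3² gives 138; the exact *t* calculation gives 139 (power 80.2%), which reproduces the plan.
- Two-sided: 175, or 176 by exact *t*. Whether the test is one- or two-sided is a separate matter.

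A constant consent delay in both arms leaves the difference and the power unchanged. If consent time varies independently of LOS, with SD equal to *r* times the LOS SD (assumed), the effect size becomes 0.3/√(1 + *r*²). One-sided power at 139 per group is then:

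| *r* | Effect size | Power |
|---|---|---|
| 0 | 0.300 | 80% |
| 0.25 | 0.291 | 78% |
| 0.5 | 0.268 | 72% |
| 1 | 0.212 | 55% |

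Entry would also be limited to patients recovered enough to consent and still in the unit when approached.

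**The case against.** The strongest reply is that the protocol states no consent time at all, and that the postoperative reading rests on one defective line. On that view the protocol needs only a clarification. It is true that both times are implied. But if criterion 3 is set aside as a drafting slip, the preoperative reading remains, and with it the one-sided removal of PONV in criterion 2.

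Three stronger readings are tempting, and the documents do not support them:

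- *Staff know the arm throughout anaesthesia and surgery.* The form marks the patient as a participant; nothing says that it shows the arm or that operating-room staff are told. The envelope is removed after consent, and later opening is not excluded. What stands is that no later trigger is planned, so early disclosure is possible.
- *Consent minutes in the PACU could mimic or hide a coffee effect.* Consent precedes allocation, so its duration cannot depend on the arm and shifts no expected difference. Consent may also run alongside recovery without lengthening the stay.
- *The two sites follow different sequences.* Nothing shows this. The text only permits it.

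**Conclusion.** The conflict is real, and the Withdraw Criteria and the intervention section must be reconciled. The main consequence belongs to the preoperative reading: PONV before coffee is deleted from one arm and counted in the other. At the assumed rates this roughly halves the apparent PONV rate with coffee when coffee does nothing. That size rests on those rates and on reading removal from the study as exclusion from analysis. A contribution to the LOS result is possible but cannot be sized from the documents.

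On the PACU reading the cost is noise and selection, with power between 78% and 55% over the assumed range of *r*, and no expected shift between arms. Early knowledge of the arm is an avoidable risk, not a documented event. The protocol should be amended on this point; confidence is medium because both consent times are inferred.

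**What to change.** State one sequence for both sites:

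1. Obtain written consent before surgery.
2. Print the Subject ID on the outside of the sealed envelope and on the data form, and send both to the PACU. The ID is then available without opening the envelope.
3. Open the envelope only when return of the gag reflex is recorded (the protocol's existing point for offering coffee) and no PONV has occurred. Record the time and treat it as randomisation.
4. Replace withdrawal criteria 2 and 3 in full with one pre-randomisation exclusion, applied to everyone: PONV before envelope opening. Deleting only the consent wording in criterion 3 would leave a rule that removes control patients with PONV, and so the events Hypothesis 2 needs.
5. Keep all PONV after opening, in both arms, as outcome data for Hypothesis 2.
6. Define the start and stop of LOS identically for both arms.
7. Count the 300 as randomised patients.

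The cost is a protocol amendment, relabelled envelopes and a line in the nurse education already planned. There are four downsides. The envelope is opened at the bedside. Some consented patients are never randomised: with early PONV at the assumed 5% to 10%, 300 randomised needs 300/0.95 = 316 to 300/0.90 = 334 consented, before other losses. Their unopened envelopes must be logged. The PONV result applies only to patients free of PONV at randomisation, and the report should say so.

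### In an open-label trial, nausea and satisfaction have no named recorder, common question, assessment times or satisfaction procedure, so H2 and H3 can differ through asking and reporting

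*Combined protocol and SAP*

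**What the plan says.** All references are to the combined protocol and SAP.

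- Study Design: "A randomized, non-blinded, controlled study will be conducted, with two arms".
- Data Collection: all department nurses involved in care are trained before the start. "This education will include information about the study design, the intervention, and the inclusion/exclusion criteria". Outcome assessment is not among the listed topics.
- Intervention or experimental aspect of the study: "A data collection form will accompany patient to the PACU designating them as a study participant". Then: "Data will be recorded directly on this form and collected by a study team member after the patient is discharged". The person who records is not named, and the form's items are not listed.
- Same section, Arm 1: "Coffee will be offered to the patient in the PACU once the patient's gag reflex has been restored following their procedure". Arm 2 gets no offer, and no matching contact is described.
- Dependent variables: the PONV outcome is "Whether the patient experienced PONV". Satisfaction is named without an instrument, a time or an administrator.
- Statistical Analysis: for H2, "a Chi Square test will be used to compare occurrence of postoperative nausea and vomiting"; for H3, "an independent samples t-test will be used to compare mean patient satisfaction for patients who received coffee".
- Withdraw Criteria: an Arm 1 patient is removed for drinking under 50 ml (criterion 1) or for PONV before coffee (criterion 2). The only control-arm removal is for PONV before or during consent (criterion 3).

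**The concern.** Nausea is a symptom that someone must ask about or the patient must volunteer, and satisfaction is an opinion. Patients and staff know the arm. The protocol describes no common question, fixed times or separation from treating staff, so three routes to a spurious difference stay open:

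- nausea may be asked about more often in one arm;
- staff who have been taught the study may judge borderline nausea in line with what they expect;
- patients may give a courteous satisfaction answer to, or in front of, whoever brought or withheld the coffee.

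The planned chi-square and t-test cannot separate any of these from an effect of coffee. The protocol does not let one say which route would dominate or in which direction.

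**Working it through.** **Inputs.** From the protocol: 139 per group (Sample Size Determination) and α = 0.05 for each hypothesis. Sidedness is not stated; I use two-sided. The protocol gives no PONV rate, recording accuracy or satisfaction SD, so these are assumptions shown over a range.

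**The plan's own figure.** The 139 per group is for length of stay (d = 0.3, power 0.8, α = 0.05). A one-sided t-test gives 138.07, rounded up to 139, so the figure reproduces. A two-sided test would need 176. This has no bearing on the present point beyond supplying n; the plan gives no sample size or power figure for H2 or H3.

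**H2, a gap in recorded rates with no true difference.** With recorded rates p₁ and p₂, n = 139 per arm and p̄ = (p₁ + p₂)/2:

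- s₀ = √[p̄(1 − p̄) × 2/n], s₁ = √[(p₁(1 − p₁) + p₂(1 − p₂))/n]
- P(significant) = Φ[(|p₁ − p₂| − 1.96 s₀)/s₁] + Φ[(−|p₁ − p₂| − 1.96 s₀)/s₁]

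For 10% versus 15%: s₀ = √(0.125 × 0.875 × 2/139) = 0.0397 and s₁ = √[(0.09 + 0.1275)/139] = 0.0396. Then (0.05 − 0.0778)/0.0396 = −0.70, and the probability is 0.242. Simulating 200,000 trials with the Pearson chi-square also gives 0.242. The same simulation gives 0.194 for 15% versus 20%, 0.343 for 5% versus 10%, and 0.048 for equal rates of 10%.

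**H2, the gap expressed as recording sensitivity.** Recorded rate = true rate × sensitivity. At a true rate of 10%, sensitivities of 0.9 and 0.7 give recorded rates of 9% and 7%. The same formula gives:

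| Sensitivity, one arm v the other | True PONV 10% | 20% | 30% |
|---|---|---|---|
| 0.9 v 0.9 | 5% | 5% | 5% |
| 0.9 v 0.8 | 6% | 7% | 9% |
| 0.9 v 0.7 | 9% | 15% | 22% |
| 0.9 v 0.6 | 16% | 29% | 44% |

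The result is the same whichever arm has the lower sensitivity.

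**H3, a pure reporting shift of δ SD.** Noncentral t with 276 degrees of freedom and noncentrality δ√(139/2) = 8.337δ. For δ = 0.1 the noncentrality is 0.83 and P(significant) is 0.132. For δ = 0.2 it is 1.67 and P(significant) is 0.383.

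**Why the H2 remedy must also settle who is analysed.** The envelope is drawn after written consent, so criterion 3 acts before the arm is known, while criterion 2 removes Arm 1 patients after randomisation. Take 150 per arm (300 split equally) and a true PONV rate of 20% in both arms, with half of Arm 1 events before coffee. Arm 1 has 30 events; 15 of those patients are removed, leaving 15/135 = 11.1%. Arm 2 keeps 30/150 = 20%. H2 is then significant in 54% of trials. At true rates of 10% and 30% the figures are 33% and 67%. If a quarter of Arm 1 events precede coffee, they are 11%, 15% and 19% at true rates of 10%, 20% and 30%. More thorough nausea checks would find more such patients, so better checks alone could enlarge this imbalance.

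**The case against.** The strongest reply is that much of the mechanism is inferred. The recording sentence is in the passive. That PACU nurses complete the form, and that both outcomes are on it, is the natural reading but is not stated. The form itself is not in the documents, so what is known is the protocol's silence, not that a common question is absent. This stands, and the point is worded accordingly.

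A reader might go further and infer that the coffee offer draws out nausea reports in Arm 1 only, and so works against coffee. The documents do not support this. Nothing rules out nausea checks in Arm 2. A patient who refuses coffee because of nausea is removed under criteria 1 and 2, so that report leaves the Arm 1 count and does not add to it. That removal favours coffee.

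The magnitudes can also be challenged, because they are rejection rates at chosen gaps. If the gap comes only from missed events, 10% versus 15% means that one arm captures at most two-thirds of what the other does. No document supports a gap of that size. This is fair, and it is why the smaller gaps are shown beside it.

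On H3, the Purpose of Study section expects coffee to make patients feel cared for, so a response to knowingly receiving it is partly the intended effect. Only the courtesy component is bias that a better procedure can reduce.

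**Conclusion.** The concern holds in a limited form. Two subjective secondary outcomes in an open-label trial have no described recorder, common nausea question, assessment times or satisfaction procedure, so H2 and H3 are open to differential asking and reporting. Size and direction are unknown. Under the assumed gaps, the chance of a significant H2 with no true difference runs from 6% (sensitivity 0.9 versus 0.8, true rate 10%) to 44% (0.9 versus 0.6, true rate 30%), against a nominal 5%. For H3 it is 13% to 38% for shifts of 0.1 to 0.2 SD.

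A reader might conclude that the H2 and H3 results could not be interpreted at all. That is too strong: vomiting is observable, the open-label design is declared, and the primary outcome is not part of this point. The change should be made because the exposure is real and the remedy is cheap.

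**What to change.** 1. **H2, recording.** Put the same nausea question on the form, with vomited yes/no and antiemetic given yes/no, at the same routine check times from PACU entry in both arms. Name the recorder. Derive PONV from these entries by one written rule.
2. **H2, analysis set.** Compare the arms as randomised and keep every randomised patient, including Arm 1 patients with nausea before coffee or who drink under 50 ml. Continue their form to discharge. Without this, the added checks would feed the one-sided removal under criterion 2.
3. **H3.** Name the satisfaction item. Have the patient complete it alone on a card that carries only the subject ID, seal it, and have the study team member collect it with the form. This reduces courtesy answers; it cannot remove the patient's own knowledge of the arm.

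Cost: a revised form, a card and an amended analysis paragraph, with no extra staff. The downside is a few seconds per check and some blank cards, which should be counted and reported by arm.

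### The primary length-of-stay test uses neither site nor procedure: a missed precision gain of unknown size, not an error, and adjustment alone would not repair the Arm 1 removals

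*Combined protocol and SAP*

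**What the plan says.** - **Primary test.** Statistical Analysis, Hypothesis 1: "an independent samples t-test will be used to compare mean length of stay in the PACU for patients who received coffee" with those who did not, at alpha 0.05. No covariate or stratification factor is named, and sidedness is not stated.
- **Sites.** Setting for the study: "In April 2022, the Bethesda Surgery Center was added as a second recruitment site". The first centre's list includes "Hysteroscopies, Uterine Ablations, Bladder Slings, Female Sterilization", none of which is named at the second. The second centre's list includes "Eye Muscle Repair, Breast Reductions and Augmentations, Abdominoplasty"; of these, only the breast procedures are also named at the first. Hemorrhoidectomy too is named only at the second. Hernia repair, laparoscopic cholecystectomy, lipoma removal, breast and other plastic surgery appear at both. Both lists are given as not exhaustive.
- **Design.** Study Design: "A randomized, non-blinded, controlled study will be conducted, with two arms". The sealed-envelope procedure under Data Collection describes no stratification by site or procedure.
- **Other variables.** The only listed potential confounders are the time at which coffee was drunk and the amount. The independent variable is "Whether patient consumed part or all of the coffee in the PACU or not".
- **Removals.** Withdraw Criteria: "Participants in the intervention arm who fail to drink at least 50 ml of coffee" are taken out, as are "Participants in the intervention arm who experience PONV prior to coffee consumption". The only control-arm rule concerns nausea and vomiting up to the end of consent.

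**The concern.** Time in recovery plausibly varies with the operation and with local discharge practice. If it does, an unadjusted comparison leaves that variation in the error term, and the confidence interval for the primary effect is wider than it need be. The protocol was changed to admit a second centre, but the analysis makes no use of site.

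The two variables listed as confounders cannot fill the gap. Both arise after randomisation and exist only for patients who drink coffee, so neither is a baseline covariate.

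Timing matters because the trial is not blinded. Covariates chosen after length of stay has been seen by arm would carry little weight, so the choice must come first.

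**Working it through.** **Inputs from the documents** (Sample Size Determination): effect size 0.3, power 0.8, alpha 0.05, 139 per group (278 in total), about 300 to be enrolled.

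**Inputs not in the documents:** R2, the standard deviation of length of stay, the site split and the procedure mix. These are assumed and shown as ranges.

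**1. The plan's own figure.** With the noncentral t distribution and noncentrality 0.3 × sqrt(n/2), 80% power needs 139 per group one-sided and 176 two-sided. The stated 139 is therefore reproduced as a one-sided calculation. Power at 139 per group is 80.2% one-sided and 70.3% two-sided. Both are carried below because sidedness is not stated.

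**2. Site and procedure together, taken as 6 terms.** With k terms and N patients:

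- effective d = 0.3 / sqrt[(1 − R2) × (1 + k/(N − k − 3))]
- degrees of freedom = N − 2 − k

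The second factor is the cost of chance imbalance in the covariates. Example for N = 278, k = 6, R2 = 0.10: 0.90 × (1 + 6/269) = 0.920, square root 0.959, effective d = 0.3/0.959 = 0.313, noncentrality 0.313 × sqrt(139/2) = 2.61 on 270 degrees of freedom, two-sided power 73.8%.

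| R2 (assumed) | Two-sided power | One-sided power | CI width vs unadjusted |
|---|---|---|---|
| Unadjusted | 70.3% | 80.2% | 100% |
| 0 | 69.3% | 79.5% | 101.1% |
| 0.01 | 69.8% | 79.8% | 100.6% |
| 0.05 | 71.5% | 81.2% | 98.6% |
| 0.10 | 73.8% | 83.0% | 95.9% |
| 0.20 | 78.7% | 86.7% | 90.4% |
| 0.30 | 83.8% | 90.4% | 84.6% |

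Break-even is at R2 of about 0.022. If all 300 are analysed (150 per arm), two-sided power is 73.6% unadjusted and 72.7%, 74.9%, 77.1% and 81.7% at R2 of 0, 0.05, 0.10 and 0.20.

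**3. Site alone (k = 1, N = 278).** R2 = p(1 − p) × delta², where p is the second site's share and delta the site difference in SD units.

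- delta = 0: R2 = 0, two-sided power 70.1%, a loss of about 0.2 points.
- p = 0.10, delta = 0.25: R2 = 0.09 × 0.0625 = 0.0056, power 70.4%, a gain of about 0.1.
- p = 0.50, delta = 0.5: R2 = 0.25 × 0.25 = 0.0625, power 72.9%, a gain of about 2.6.

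Break-even is at R2 of about 0.004.

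**4. Do the covariates repair the removals?** If a share f of Arm 1 is removed and would have stayed delta SD longer, the coffee mean falls by about f × delta with no true effect: 0.10 × 0.5 = 0.05 SD, or 0.10 × 1 = 0.10 SD. This was simulated with 8,000 trials per setting, no coffee effect, 150 per arm, a 30% second-site share, six procedure groups and R2 about 0.10. Each patient was flagged with probability 10%, unrelated to site or procedure, and flagged patients were dropped from Arm 1 only. One-sided false-positive rates:

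| Flagged patients' extra stay | t-test, removals applied | Adjusted, removals applied | Everyone kept by assigned arm |
|---|---|---|---|
| 0.5 SD | 10.9% | 11.4% | about 5%, adjusted or not |
| 1 SD | 19.8% | 21.1% | about 5%, adjusted or not |

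Adjustment leaves the bias where it was, and the smaller standard error raises the error rate slightly. Keeping everyone by assigned arm removes it.

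**The case against.** The strongest reply is that nothing here is wrong. Under randomisation an unadjusted t-test on all patients by assigned arm is valid, and one simple prespecified test is a reasonable choice for a small single-system study. No section promises adjustment or stratification. That stands, and it is why this is a precision point only.

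The benefit also rests wholly on an assumed R2. The procedure lists overlap, are not exhaustive, and show neither the enrolled mix nor any difference in length of stay. That stands too. The documents support neither a claim that the gain is small nor a claim that it is large: below R2 of about 0.022 six terms cost power, and 0.30 cannot be excluded.

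A third reply is that procedure may not be available. It is not among the listed variables, data forms carry only a subject ID, and the form itself is not in the documents. This limits the change but does not defeat it, because site is known at enrolment.

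Two stronger readings are tempting:

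- A reader might infer that opening a second site partway through confounds the comparison. The documents do not support this. Assignment comes from sealed envelopes, and no passage ties arm to site; without stratification, imbalance would arise by chance.
- A reader might infer that adding site and procedure makes the planned comparison sound. It does not. That comparison is by coffee received, after removals that fall on Arm 1 with no matching rule for controls in the PACU.

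**Conclusion.** The point holds as a minor one. The primary analysis omits two baseline factors that may predict length of stay, and this is a missed precision gain rather than a flaw in validity. With 6 terms at 139 per group, two-sided power changes by −1.0 points at R2 = 0, +3.5 at 0.10, +8.4 at 0.20 and +13.5 at 0.30. With site alone the range examined is −0.2 to +2.6 points. These figures assume the protocol's effect size of 0.3 and a linear model; R2 is assumed throughout.

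The removal bias is a separate and more consequential matter. The simulated false-positive rates show only that covariates do not cure it; they do not measure the cost of leaving site and procedure out. They also assume that removal is unrelated to site and procedure. If it were related, adjustment could take out part of the bias.

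**What to change.** Before any length-of-stay data are examined by arm:

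1. Make the Hypothesis 1 primary analysis a linear model of length of stay on randomised arm and site. Add a few prespecified procedure groups, based on the procedure scheduled before randomisation, if that is recorded for all subjects; otherwise use site alone.
2. Fit it to all randomised patients by assigned arm, and keep recording length of stay for those now taken out under the Withdraw Criteria.
3. Report the adjusted mean difference with its 95% CI, and keep the unadjusted t-test on the same patients as supporting.
4. Leave time to coffee and amount of coffee out of the model.
5. Confirm that site and scheduled procedure are captured for each subject.

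If length of stay has already been examined by arm, label the adjusted model post hoc and do not make it primary.

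**Cost.** One linear model in SPSS, a few degrees of freedom, and about 1 point of power if the covariates explain nothing. The listed start is April 2018, so any patients enrolled before April 2022 are all from the first site. Their procedure may need chart look-up through a subject-ID link that the plan does not describe.
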